5.4 General Concomitant Medication and Supportive Care Guidelines

Because there is a potential for interaction of itraconazole and hydroxychloroquine with other concomitantly administered drugs through the cytochrome P450 system, the case report form must capture the concurrent use of all other drugs, over-the-counter medications, or alternative therapies. The Principal Investigator should be alerted if the patient is taking any agent known to affect or with the potential to affect selected CYP450 isoenzymes.

The patient may not take any other anti-cancer or investigation therapy while on study. Radiation therapy for palliative reasons may be permitted for palliative measures such a relief from pain or bleeding while the patient is on study, except for brain metastases. Itraconazole will be held for one week prior to radiotherapy. Patients who are found to have brain metastases requiring radiotherapy while on study will be discontinued from study treatment.

For list of prohibited drugs refer to Appendix C

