3. PATIENT SELECTION

3.1 Inclusion Criteria

- 3.1.1 Patients aged 18 years or older with histologically or cytologically confirmed epithelial ovarian cancer.
- 3.1.2 Platinum-resistant or refractory disease defined as a radiological or clinical progression less than six months after having finished platinum-based chemotherapy.
- 3.1.3 ECOG performance status equal to or less than 1.
- 3.1.4 Patients must have clinically or radiographically documented measurable disease. Radiographic measurable disease is defined as at least one site of disease that is unidimensionally measurable as follows [46]:

○ CT-scan, physical exam
 ○ Chest X-ray
 ○ Lymph node short axis
 ≥10 mm
 ≥20 mm
 ≥15 mm

- All radiology studies must be performed within 28 days prior to registration (35 days if negative).
- 3.1.5 All systemic therapy must have been completed ≥ 4 weeks prior to enrollment with radiologic evidence of disease progression.
- 3.1.6 Life expectancy should be more than 3 months.
- 3.1.7 Patients receiving any medications or substances that are inhibitors or inducers of CYP3A4 are ineligible. Because the lists of these agents are constantly changing, it is important to regularly consult a frequently-updated list such as http://medicine.iupui.edu/clinpharm/ddis/table.aspx; medical reference texts such as the Physicians' Desk Reference may also provide this information.
- 3.1.8 Laboratory Requirements within 7 days prior to enrollment:

Haematology: hemoglobin ≥90 g/L

 $\begin{array}{ll} absolute \ neutrophils & \geq 1.5 \times 10^9/L \\ platelets & \geq 100 \times 10^9/L \end{array}$

Biochemistry: bilirubin within normal limits

AST(SGOT) $\leq 2.5 \times \text{institutional upper limit of normal}$

/ALT(SGPT)

serum creatinine within normal limits

or

creatinine clearance ≥60 mL/min/1.73 m² for patients with creatinine levels

above institutional normal

- 3.1.9 Subjects with treated and asymptomatic brain metastases are eligible. Patients that received palliative radiation (for brain metastases) are eligible if they have been asymptomatic for at least 2 weeks with use of maintenance steroid therapy, and last received radiation at least 4 weeks prior to start of therapy.
- 3.1.10 Patients must have the ability to understand and willing to sign a written informed consent document.

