5.2 Definition of Dose Limiting Toxicity

Toxicity will be graded using CTCAE version 4.0, with dose limiting toxicities being assessed during the first 28 days of treatment (cycle 1). Any dose limiting toxicity must be a toxicity that is considered related to study drug. Patients is considered evaluable for DLT assessment if < 7 days of full dose (according the specific dose level) treatment have been omitted. If at any day the treatment will not be assumed at full dose, it will be considered as omitted.

Dose limiting toxicity is defined as follows:

Haematologic:

- Absolute neutrophil count (ANC) $< 0.5 \times 10^9/L$
- Febrile Neutropenia (ANC $<1.0 \times 10^9$ /L, fever $\ge 38.5^\circ$ C)
- Platelets $<25 \times 10^9/L$
- Bleeding felt to be due to thrombocytopenia

Non-Haematologic:

- Diarrhea ≥ Grade 3 despite optimal loperamide use.
- Rash \geq Grade 3 or grade 2 if medically concerning or unacceptable to the patient.
- Other grade >3 effects thought to be treatment related.
- Missing >14 days of treatment for toxicity reasons.

Ocular Toxicity

Any occurrence of ocular toxicity that is greater than grade 1, including but not limited to retinopathy is considered to be a dose-limiting toxicity and the patient must discontinue the study medications.

Any Toxicity

Patients experiencing adverse events \geq grade 2 that do not recover within 2 weeks, despite optimal supportive management and treatment interruption.

Management and dose modifications associated with the above adverse events are outlined in Section 7.

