11.1.2 Disease Parameters

Measurable disease. Measurable lesions are defined as those that can be accurately measured in at least one dimension (longest diameter to be recorded) as ≥ 20 mm by chest x-ray or as ≥ 10 mm with CT scan, MRI, or calipers by clinical exam. All tumor measurements must be recorded in millimeters (or decimal fractions of centimeters).

Note: Tumor lesions that are situated in a previously irradiated area might or might not be considered measurable. This will be determined by the investigator, and documented in source.

Malignant lymph nodes. To be considered pathologically enlarged and measurable, a lymph node must be ≥15 mm in short axis when assessed by CT scan (CT scan slice thickness recommended to be no greater than 5 mm). At baseline and in follow-up, only the short axis will be measured and followed.

Non-measurable disease. All other lesions (or sites of disease), including small lesions (longest diameter <10 mm or pathological lymph nodes with ≥10 to <15 mm short axis), are considered non-measurable disease. Bone lesions, leptomeningeal disease, ascites, pleural/pericardial effusions, lymphangitis cutis/pulmonitis, inflammatory breast disease, and abdominal masses (not followed by CT or MRI), are considered as non-measurable.

Note: Cystic lesions that meet the criteria for radiographically defined simple cysts should not be considered as malignant lesions (neither measurable nor non-measurable) since they are, by definition, simple cysts.

'Cystic lesions' thought to represent cystic metastases can be considered as measurable lesions, if they meet the definition of measurability described above. However, if non-cystic lesions are present in the same patient, these are preferred for selection as target lesions.

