11.1.4.1 Evaluation of Target Lesions

Complete Response (CR): Disappearance of all target lesions. Any pathological lymph nodes (whether target or non-target) must have reduction in short axis to <10 mm.

Partial Response (PR): At least a 30% decrease in the sum of the diameters of target lesions, taking as reference the baseline sum diameters.

Progressive Disease (PD): At least a 20% increase in the sum of the diameters of target lesions, taking as reference the smallest sum on study (this includes the baseline sum if that is the smallest on study). In addition to the relative increase of 20%, the sum must also demonstrate an absolute increase of at least 5 mm. (Note: the appearance of one or more new lesions is also considered progressions).

Stable Disease (SD): Neither sufficient shrinkage to qualify for PR nor sufficient increase to qualify for PD, taking as reference the smallest sum diameters while on study, including baseline. Note that patients are not able to go from PR to SD.

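### Palliative radiotherapy is allowed on treatment, but the response rules make no exception for a target lesion irradiated after baseline, so shrinkage due to radiation may count as an objective response

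*Protocol*

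**What the plan says.** **Radiotherapy during treatment.** Section 5.4 states: "Radiation therapy for palliative reasons may be permitted for palliative measures such a relief from pain or bleeding while the patient is on study". The exception is the brain: "Patients who are found to have brain metastases requiring radiotherapy while on study will be discontinued from study treatment". No equivalent rule exists for other sites.

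**Response.** Section 11.1.2 fixes the target lesions at baseline (at most five, chosen mainly by size) and adds all of them into the sum. Section 11.1.4.1 defines partial response as "At least a 30% decrease in the sum of the diameters of target lesions, taking as reference the baseline sum diameters". Section 11.1.4.3 takes the best response between treatment start and progression. None of these sections mentions radiotherapy given during that period.

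**Radiotherapy before entry.** Section 11.1.2 says: "Tumor lesions that are situated in a previously irradiated area might or might not be considered measurable". It continues: "This will be determined by the investigator, and documented in source". The eligibility intervals in section 3.1 cover systemic treatment ("All systemic therapy must have been completed ≥ 4 weeks prior to enrollment with radiologic evidence of disease progression") and, in 3.1.9, palliative brain radiation ("last received radiation at least 4 weeks prior to start of therapy"). No interval is given for radiotherapy to other sites. Section 10 lets the baseline scan precede treatment by up to 28 days.

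**The concern.** Section 5.4 creates an event that section 11 does not handle. If a target lesion is irradiated and shrinks, the stated rules credit that shrinkage to the drug combination. There is no control arm in which a local-treatment effect would also appear. Section 13.2 rests both phase II decisions on the count of responses, and under sections 13.1.2 and 13.2 a single response among 9 patients opens stage 2.

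Section 13.5.2 keeps all eligible patients in the main response analysis. Permitted radiotherapy is not a protocol deviation, so the sub-analyses described there would not remove such a patient either.

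**Working it through.** **1. Following the rules as written.** A patient has a non-brain target lesion irradiated after the baseline scan and stays on treatment.
- The lesion remains in the sum (11.1.2).
- If the sum falls by 30% from baseline, the definition of PR is met (11.1.4.1). For example, if the irradiated lesion is 60% of the baseline sum and halves while the rest is unchanged, the sum changes by 0.6 × 0.5 = 30%.
- A confirmatory scan at least 4 weeks later (11.1) will still show the shrinkage if it lasts.
- If no new lesion or non-target progression appears, best overall response is PR (11.1.4.3).

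Radiotherapy between the baseline scan and day 1 leads to the same result, because the reference sum was measured before it.

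**2. The plan's own figures.** Section 13.2 states α = 0.05 and power 0.81 for 15% versus 35%, with 9 + 25 patients. (The text ties the 0.81 to a true rate of 20%.) Exact binomial results:
- Printed rule, read literally (at least 1 of 9, then at least 8 of the 25): α = (1 − 0.85⁹) × P(Bin(25, 0.15) ≥ 8) = 0.768 × 0.0255 = 0.020. Power at 35% is 0.680.
- At least 2 of 9, then at least 9 of 34 in total: α = 0.047, power at 35% is 0.811, and expected size under the null is 19.0. This reproduces the stated 0.05, 0.81 and 19. Its expected size under the alternative is 31.0, not the stated 25.

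This mismatch is a separate matter. Both rules are carried forward because the protocol does not settle which applies.

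**3. Effect of counting radiation-driven responses.** Let f be the share of patients irradiated at a target lesion and c the chance that this turns a non-responder into a recorded responder. Both are assumptions. The apparent rate under the null is p = 0.15 + 0.85 × f × c.

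| f | c | p | ≥2/9, then ≥9/34 | printed rule |
|---|---|---|---|---|
| 0 | – | 0.150 | 0.047 | 0.020 |
| 2% | 25% | 0.154 | 0.055 | 0.023 |
| 5% | 25% | 0.161 | 0.068 | 0.029 |
| 5% | 50% | 0.171 | 0.094 | 0.042 |
| 10% | 25% | 0.171 | 0.094 | 0.042 |
| 10% | 50% | 0.193 | 0.160 | 0.078 |

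The last two columns give the probability of declaring the combination active when the true drug response rate is 15%.

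**4. Stage 1.** Under the printed gate, the chance of passing at a true 15% is already 1 − 0.85⁹ = 0.768. At p = 0.154 to 0.193 it is 0.779 to 0.854.

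**The case against.** The strongest reply is that the route is narrow. The whole sum must fall by 30%, the fall must be confirmed, and progression anywhere else overrides it. Worsening pain or bleeding may be judged clinical progression, which ends treatment under section 5.5; under footnote g of the section 10 calendar, no further scans are then required. Section 11.1.8 adds central radiology review. All of this is true and makes the event less frequent. None of it separates a radiation effect from a drug effect, and the central reader has no rule to apply.

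It can also be said that concomitant local treatment belongs in the SAP. Here section 11 sets the response criteria itself and in detail, so the gap is in the protocol's own text.

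The objection to the numbers stands. Both rates are assumed, and at the low end (2% and 25%) the change is only from 0.047 to 0.055. Under the printed stage 1 gate, most of the chance of continuing is there without any radiotherapy.

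Three stronger readings are not supported:
- A reader might infer that lesions irradiated before entry always stay in the target sum. Section 11.1.2 leaves this to the investigator; the fault there is discretion without a criterion.
- A reader might assume that the irradiated lesion will usually be the dominant target. The protocol does not say so.
- A reader might see a conflict between the one-week itraconazole hold in section 5.4 and section 5.2, where "If at any day the treatment will not be assumed at full dose, it will be considered as omitted". A cycle 1 patient with 7 omitted days is simply not evaluable for DLT. That is coherent.

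**Conclusion.** The point holds in a limited form. The protocol permits non-brain palliative radiotherapy on treatment and has no response rule for a target lesion irradiated after the baseline scan, so shrinkage caused by radiation may count as an objective response. For lesions irradiated before entry, measurability is left to judgement without a criterion. No passage covers non-brain radiotherapy between the baseline scan and day 1.

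The size of the bias cannot be taken from the documents. For assumed rates of 2-10% irradiated and 25-50% converted, the false-positive probability is about 0.055-0.16 against 0.047, or 0.023-0.078 against 0.020 under the printed rule. These figures illustrate the direction and possible scale; they are not estimates. The gap should be closed because response rate is the only basis for the phase II decisions and the change is small.

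**What to change.** Leave the clinical permission for radiotherapy as it is, and add measurement rules.

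- **Sections 11.1.2 and 11.1.4:** a target lesion irradiated after the baseline scan, at any site and including before day 1, cannot contribute to CR or PR from that date. Only scans before radiotherapy count towards best response, and a patient with no response recorded by then is a non-responder. Growth of the irradiated lesion, non-target progression and new lesions still count as PD.
- **Section 11.1.2:** replace the open wording on previously irradiated areas with an objective criterion: such a lesion may be a target only if it has progressed since radiotherapy.
- **Case report form:** record radiotherapy site and dates. Section 5.4 requires capture of other drugs, over-the-counter products and alternative therapies, but does not name radiotherapy.

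The cost is a few sentences and one added CRF entry. A few patients may lose a response that appears only after radiotherapy.

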5.4.1 Patients with Diabetes Mellitus

Patients with diagnosis of diabetes mellitus treated with insulin or oral hypoglycemic drugs needs to carefully monitor blood sugar level due to increased risk of hypoglycemia when treated with itraconazole and/or hydroxychloroquine. Patients with diabetes will be required to monitor and record the capillary blood sugar levels at least three times a day. Dose of insulin or oral hypoglycemic drugs will be adjusted accordingly.

5.5 **Duration of Therapy**

In the absence of treatment delays due to adverse event(s), treatment may continue as long as patient is benefitting or until one of the following criteria applies:

- Disease progression as defined by RECIST 1.1
- Clinical progression
- Women who become pregnant or are breast feeding
- Sexually active subjects who refuse to use medically accepted forms of contraception (e.g. male condom, female condom) during the study and for 30 days following

discontinuation of study treatment

- Intercurrent illness that prevents further administration of treatment
- Unacceptable adverse event(s)
- Significant non-compliance with the protocol schedule in the opinion of the investigator
- Patients requiring a delay in treatment beyond the allowed time frame
- Patients requiring more than 2 dose reductions of hydroxychloroquine or itraconazole
- Patient decides to withdraw from the study
- General or specific changes in the patient's condition render the patient unacceptable for further treatment in the judgment of the investigator
- Termination of the protocol by a regulatory agency or Sponsor-Investigator, or study medication can no longer be provided

5.6 **Duration of Follow Up**

Patients will be followed for 12 weeks after removal from study or until death, whichever occurs first. Patients removed from study for unacceptable adverse event(s) will be followed every 4 weeks by the clinic team until resolution or stabilization of the adverse event.

		Follow-Up Period			
		30-37 Days from the End of Study Drug Administration	Every 4 weeks (after the off study visit), up to 12 weeks	Until resolution or stabilization of treatment related adverse event(s)	RECIST 1.1 every 12 weeks from last scan until PD
from	Objective Disease Progression	X	X	X (FU every 4 weeks)	
Reason Patients Removed from study	Clinical Progression/ Symptomatic Deterioration	Х	Х	X (FU every 4 weeks)	
son Patient str	Adverse Events or clinically significant lab value	Х	X	X (weekly FU for 4-weeks, then monthly)	X
Reas	All other patients	X	X	X (FU every 4 weeks)	X

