2.2.2 Hydroxychloroquine

Mechanism of Action

Hydroxychloroquine interferes with digestive vacuole function within sensitive malarial parasites by increasing the pH. It is hypothesized to inhibit autophagy by acting on the autophagolysosome [7]. This has been demonstrated in a phase I trial of hydroxychloroquine and temsirolimus in patients with advanced solid tumors and melanoma. In this study, hydroxychloroquine was administered in incremental levels with a fixed dose of temsirolimus and an increase in autophagic vacuoles was demonstrated with electron microscopy in peripheral blood mononuclear cells [31].

Clinical Trials in Oncology

Clinical trials have been conducted to investigate the efficacy and safety of chloroquine and its derivatives in combination with traditional chemotherapy. In a study of chloroquine in adjuvant therapy for treatment of glioblastoma multiforme, the mean survival time of patients receiving chloroquine was significantly longer than patients treated with conventional therapy [32].

Safety issues have been raised when combining hydroxychloroquine with chemotherapy. A phase I study using high-dose hydroxychloroquine and dose-intense temozolomide to treat advanced solid malignancies was considered to be safe and tolerable [31]. A similar conclusion has been drawn in a study which combined temsirolimus and hydroxychloroquine for solid malignancies. The 1200 mg/day hydroxychloroquine with temsirolimus was demonstrated to be safe and effective in the clinic [33]. However, another study using hydroxychloroquine in combination with radiation therapy and temozolomide for newly diagnosed glioblastoma indicated that hydroxychloroquine 600 mg/day was the maximum tolerated dose, but autophagy was not achieved consistently in patients and overall survival was not significantly improved [34].

Pharmcokinetics of Hydroxychloroquine

Absorption of hydroxychloroquine has been found to be incomplete and variable (~70% [range: 25 to 100%]) [35]. Hydroxychloroquine is bound to protein in the blood with approximately 40% bound to primarily albumin. The half-life of elimination is approximately 40 days and is primarily metabolized in the liver by cytochrome CYP 2D6 [36]. Hepatic metabolites include bidesethylchloroquine, desethylhydroxychloroquine, and desethylchloroquine. Approximately 15% to 25% is excreted in the urine.

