3.3 Pregnancy

Both itraconazole and hydroxychloroquine are contraindicated in pregnancy. Due to potential teratogenic effects, women of child-bearing potential must agree to use adequate contraception (hormonal or barrier method of birth control; abstinence) prior to study entry and for the duration of study participation. Should a woman become pregnant or suspect she is pregnant while she or her partner is participating in this study, she should inform her treating physician immediately.

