7.7 Pregnancy

Any pregnancy of a study subject or of a study subject's partner that occurs during study participation should be reported for pregnancies that occur up to 30 days after the last dose of study medication. If the study subject is the father, then two SAE forms should be completed, one for the father and the other for the mother and neonate. The pregnancy should be followed up to determine outcome, including spontaneous or voluntary termination, details of birth, and the presence or absence of any birth defects, congenital abnormalities or maternal and newborn complications.

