- c: Off-study evaluation and follow up as described in section 5.5
- d: Pre-treatment biopsy to be done up to 28 days prior to start of therapy. On-treatment biopsy to be done on day 8-14.
- e: Patients undergoing a biopsy or fluid collection for diagnostic or therapeutic reasons may have a sample of their tissue or fluid collected for the purposes of this study.
- f: Patients will be followed every 4 weeks from the End of Treatment visit for 12 weeks or until resolution of adverse events for patients who will come off study due to toxicity.
- g: Only patients who come off study treatment for reasons other than progressive disease (radiological or clinical) need to have scans and RECIST measurements performed. This will occur every 12 weeks from the previous scan until documented progression (radiological or clinical).
- h: Three 10 mL tubes of heparinized blood will be collected for PBMC and plasma isolation, and one 5 mL SST tube for sera.
- i: Samples must be drawn prior to MUGA.
- j. The following eye tests will be performed: Ocular Symptom Assessment, Visual Acuity, Slit Lamp Examination, Intraocular Pressure, Dilated Fundoscopic Examination, Schirmer test and any other diagnostic test.

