APPENDIX F DATA MANAGEMENT GUIDELINES

Data Management Guidelines

Case Report Form Submission Schedule

The Registration Checklist will be a paper CRF that will be provided by the Drug Development Central Office and all other data required for the study will be collected in eCRFs in Medidata. The form submission schedule is outlined below.

Case Report Form	Submission Schedule
Registration Checklist	At the time of registration
Baseline Form	Within 3 weeks of on study date
On Treatment Form	Within 3 weeks of the end of each cycle of
	treatment
Off Treatment Form	Within 3 weeks of the patient coming off-study
Short Follow-up Form	Within 3 weeks of the patient coming to clinic.
	Required every 4 weeks until 12 weeks post off-
	treatment visit.
Final Report Form	Within 3 weeks of the patient's completion on
	study

Case Report Form Completion

The paper Registration Checklist must be completed using black or blue ink. Any errors must be crossed out so that the original entry is still visible, the correction clearly indicated and then initialed and dated by the individual making the correction. eCRFs will be completed according to the schedule noted above.

All patient names or other identifying information will be removed prior to being sent to the Central Office and the documents labeled with patient initials, study number and the protocol number if applicable.

Monitoring

This is an investigator initiated study and study monitoring will be performed by the Drug Development Program Central Office or its designate.

Data in the Medidata Rave eCRFs will be monitored on a regular basis and quality assurance measures will be performed. Electronic data queries as well as paper query letters may be issued to the site.

Regulatory Requirements

• Please submit all required documents to the DDP Central Office.

- Canadian Principal Investigators must submit a completed Qualified Investigator Undertaking. The original signed copy is to be housed by the DDP Central Office.
- All investigators must have an up-to-date CV (signed within 2 years) on file with the DDP Central Office.
- Laboratory certification/accreditation and normal ranges are required
- Confirmation of all investigators having undergone training in the Protection of Human Research Subjects is required. It is preferred that other staff involved in the trial also undergoes such training.
- Investigators and site staff are required to complete Medidata eCRF training modules depending on delegated tasks

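### The only dated limits for contraception (5.5) and pregnancy reporting (7.7) are 30 days, less than one hydroxychloroquine half-life as stated in 2.2.2

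*Protocol*

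**What the plan says.** Three sections of the Protocol bear on when these obligations end.

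- **3.3 Pregnancy** states that both drugs are contraindicated in pregnancy and gives the reason for its rule: "Due to potential teratogenic effects, women of child-bearing potential must agree to use adequate contraception". The rule applies "prior to study entry and for the duration of study participation". It gives no number of days after the last dose.
- **5.5 Duration of Therapy** lists reasons to stop treatment. One is refusal of contraception "during the study and for 30 days following" discontinuation of study treatment.
- **7.7 Pregnancy** covers any pregnancy "that occurs during study participation should be reported for pregnancies that occur up to 30 days after the last dose of study medication".

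Section 2.2.2 gives the pharmacokinetic figure: "The half-life of elimination is approximately 40 days".

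Visits continue after treatment. The Study Calendar (section 10) places the off-treatment visit 30–37 days after the last dose. The table in 5.6 then has visits "Every 4 weeks (after the off study visit), up to 12 weeks". Calendar note f agrees ("Patients will be followed every 4 weeks from the End of Treatment visit for 12 weeks or until resolution of adverse events"), and Appendix F requires a short follow-up form on the same schedule ("Required every 4 weeks until 12 weeks post off"-treatment).

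**The concern.** A contraception rule justified by possible harm to a fetus should last while a meaningful amount of drug remains. The only limits stated in days, 5.5 for contraception and 7.7 for reporting, are shorter than one half-life of the slower drug on the Protocol's own figure. No section explains the choice of 30 days.

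Two practical consequences follow. A site looking for a contraception end date will find only the 30 days in 5.5 and may advise patients accordingly. A site applying the 30 days in 7.7 may not report a pregnancy that begins while more than half of the hydroxychloroquine is still present. Such a pregnancy might never reach the sponsor, even though the patient is still attending scheduled visits.

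**Working it through.** **Inputs from the Protocol**

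- Hydroxychloroquine half-life: about 40 days (2.2.2).
- Dated limits: 30 days after discontinuation (5.5) and 30 days after the last dose (7.7).
- Off-treatment visit: day 30–37 after the last dose (section 10).
- Further 4-weekly visits: up to 12 weeks, or 84 days (5.6 table, calendar note f, Appendix F).

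**Assumptions**

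- Elimination at a single rate, so the fraction remaining at day d is 2^(−d / half-life).
- Because the half-life is stated only as approximate, 30 to 50 days is used as a range. This range is an assumption.

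The Protocol gives no figure of its own for residual drug, so there is none to reproduce.

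**Step 1: the 30-day limits.** 30 / 40 = 0.75 half-life. 2^(−0.75) = 0.595, so about 59% remains. With a half-life of 30 days it is 50%, and with 50 days it is 66%. Over this range, 30 days covers at most one half-life.

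**Step 2: the last scheduled 4-weekly visit.** 30 + 84 = 114 and 37 + 84 = 121, so it falls on day 114–121.

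**Step 3: candidate end dates**

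| Days from last dose | Half-lives (40 d) | Remaining, 40 d | Remaining, 30 d to 50 d |
|---|---|---|---|
| 30 | 0.75 | 59% | 50% to 66% |
| 114 | 2.85 | 14% | 7% to 21% |
| 121 | 3.03 | 12% | 6% to 19% |
| 200 | 5.00 | 3% | 1% to 6% |

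**Step 4: where section 3.3 may end.** Section 5.7 counts completed follow-up as a reason for removal from study. Read with calendar note f, study participation would last until about day 114–121. Section 5.6, however, speaks of 12 weeks of follow-up after removal from study, which places removal before follow-up. The Protocol therefore supports more than one reading of how long the contraception rule in 3.3 runs.

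**The case against.** The strongest counter-argument concerns contraception. Section 3.3 is the rule that imposes it, and 5.5 is only a list of reasons to stop treatment. The criterion in 5.5 also joins two periods. If being on study includes follow-up, the 30 days sets a further minimum and does not shorten 3.3. On that reading contraception already lasts to about day 114–121, which is the minimum proposed here.

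This stands as far as it goes. A reader might infer from 5.5 that the Protocol ends contraception at 30 days, but the text does not establish that. It leaves the end date open and puts a shorter number beside it. The argument also does little for reporting: 7.7 mentions study participation in the same sentence, but its only dated limit is 30 days after the last dose.

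Three further points have weight.

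- **Late harm is partly captured.** Under 7.2 a congenital anomaly is a serious adverse event. Events more than 4 weeks after study discontinuation remain reportable if a relationship to study drug is suspected. What can be missed is a late pregnancy with a normal outcome, or a loss that nobody attributes to the drugs.
- **Residual drug is not fetal risk.** No section ties contraception to a number of half-lives or a residual level. A reader might infer that five half-lives (200 days) is the correct value. The Protocol does not set it; it is a convention.
- **Few patients are likely to be affected.** The Protocol gives no number. It does provide for women of childbearing potential through 3.3, 7.7 and a serum pregnancy test in the calendar.

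**Conclusion.** The point holds in a limited form. The 30-day reporting limit in 7.7 and the 30-day figure in 5.5 are short against the Protocol's own half-life: 0.75 of a half-life, with about 59% of the hydroxychloroquine remaining (50% to 66% for an assumed half-life of 30 to 50 days). For reporting, this is a stated limit that serves its purpose poorly. For contraception, it is an unclear end date, because 3.3 may already reach about day 114–121.

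The size rests on single-rate elimination and one approximate half-life. It shows exposure, not a level of fetal risk. The consent form is not among the documents, so nothing is concluded about what patients are told. No endpoint, dose decision, alpha or power is affected. This is a cheap improvement to patient safety wording.

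**What to change.** In 3.3, 5.5 and 7.7, state the same end date for contraception and for pregnancy reporting, counted from the last dose of either drug. It should be no earlier than the last scheduled 4-weekly follow-up visit. A single figure of 121 days covers the latest such visit, at about three half-lives with about 12% remaining. Give the reason for the chosen date in one sentence that cites the half-life in 2.2.2.

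The sponsor may prefer 200 days (five half-lives, about 3% remaining). It should then be labelled as a convention, and contact after the last scheduled visit would have to be added.

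The cost of the 121-day option is wording in three sections and no new visit. If the off-treatment visit falls on day 30, the last scheduled visit is day 114 and the final 7 days (121 − 114) rest on the patient's own report. The downside is a longer contraception and reporting obligation for the women of childbearing potential in the trial.
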